## **B. Analysis of Study Results**

During the summative evaluation, data gathered is qualitative and quantitative in nature. Online survey measures will be administered at four time points (baseline, post treatment, 7-day follow up, 30-day follow up, and 90-day follow up) to all ED study patient participants and three time points (baseline, 30-day, and 90-day follow up) to all Telehealth study participants. For the ED study, provider participants will complete study procedures via interview with the researcher (on paper or online if they prefer) at post treatment for all patients they treat as part of this study. Measures for patient

participants will include demographics, questions about suicidality, depressive symptoms, use of acute crisis tolerance skills, coping with acute distress, and satisfaction with ED experience. Measures for provider participants will include demographics, questions about preparedness for clinical interview, patient distress, provider confidence in suicide risk assessment, and helpfulness of Jaspr. Semi-structured interviews will be conducted with patient participants at each time point after baseline to obtain feedback about the participant's experience in the ED, experience with suicide symptoms, and/or Jaspr tools and features. For the Telehealth study, measures for patient participants include demographics, questions about suicidality, depressive and anxiety symptoms, stress, coping with acute distress, satisfaction with outpatient care and JAH. Semi-structured interviews at each follow-up assessment will be conducted to obtain feedback about the participant's experience with suicide and use of their resources since the prior study session.

Data will be entered online using an encrypted, secure online assessment tool such as SurveyMonkey. Missing values are coded as to reason missing (e.g., 'participant unable to be located,' 'participant refused to answer,' etc.). All data will be cleaned for logic and other types of errors using SPSS. With regards to dropouts and missing data, we plan to gather data for all participants at all time points, including from those who stop using Jaspr or JAH. This will allow us to conduct primary analyses on the intent-to-treat sample. To minimize missing data, we have included built-in incentives (i.e., bonus payments for completing all assessments) and training by [name] in methods to decrease attrition. To the extent that there is question about skipped or missed assessments, the software and analysis method we have chosen provides options for the handling of incomplete data. Preference will be given to those methods for which the assumptions (e.g., Missing at Random) are plausibly met and that have the least biased parameters.

***Analysis Strategy.*** We will use SPSS Version 23. For patient data, we will use Hierarchical Linear Modeling (HLM). HLM provides greater flexibility in that it can analyze a variety of commonly encountered outcome distributions (e.g., continuous, binary count), test the fit of different covariance matrix assumptions; and include participants who are missing data at some time points. We will account for nesting of patients under providers by including providers as a random effect; we will account for nesting within sites by including dummy coded fixed effects predictors representing site in all analyses. For each outcome, we will specify the correct distribution and compare fit indices to identify the covariance matrix best fitting the data. Many hypotheses relate to change over time, and so the multiple time-points will be treated as nested within the individual. Also, we will treat the intervention conditions (Jaspr and JAH) and time as categorical, dummy-coded predictors; the control conditions and baseline scores will serve as the reference category. The parameter of interest will be the Time X Condition interaction, and the Type III statistic will serve as an omnibus test of whether the two conditions differed in change over time. Regression coefficients will indicate at which follow up time points the conditions showed differential change from baseline. For patient satisfaction as well as the secondary hypotheses concerning medical providers ratings of helpfulness, we will compute descriptive statistics and consider ratings to be favorable using the *a priori* established criteria that 80% or more respondents rate program components as favorable or highly favorable. For the remaining secondary hypotheses, which are based on provider data about patients from both conditions at one time point, we will compute between-condition means. Since it is possible that not all providers will be able to provide data given time constraints inherent in their job, we may not have the statistical power to conduct probability tests. Hence, we will examine the data descriptively to provide preliminary information about efficacy and compute effect sizes to inform future research.

***Statistical Power Considerations.*** For Hypotheses 1 and 2, we conducted power analyses focused on the ability to detect statistical significance on the key parameter of interest, the Time X Condition interaction. Power analyses assumed equal size groups,  $p \leq .05$ , power of .80, and two-tailed tests. Using GPower's utility for the General Linear Model, we found that a total sample size of 24 patients would allow detection a medium effect ( $f > = 25$ ). However, this assumes no design effects (DE) that occur due to the nesting of patients under physicians. In the likely event that design effects exist, a sample of 72 participants will allow sufficient power to detect a medium effect with DEs as great as 3.0). Adjusting this number for possible 20% attrition, we would need to enroll at least 90 patients, but will strive to include 120 patients total in this research to ensure we have sufficient statistical power for all outcome variables.

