#### ED Study

**Patient Participants:** Because the patient's medical treatment is of foremost importance and to accommodate the fluid, unpredictable environments in the ED and to work within their usual flow, the researchers will pause all research procedures whenever necessary to allow for the patient's medical care and resume should there be additional periods of waiting. Once enrollment is complete (i.e., consent is obtained), the researchers will request a release of information from the participant for information we would like to gather from a member of their care team after the patient's discharge. Specifically, we are interested in collecting data about the patient's length of stay, if physical or chemical restraints were used and if so for how long, their final discharge disposition (e.g., if the patient was admitted to inpatient, residential, or substance abuse treatment or discharged to home), and if the patient was admitted whether it was involuntary or voluntary. This data will be obtained orally by speaking with a member of the patient's care team; medical records will not be accessed by the researchers. Permission (or not) for this release of information will not impact the patient's participation in the study (i.e., if they decline to provide permission for this release, they may still participate in the study). If the patient agrees to provide permission for the researcher to collect this information, they will be asked to sign a release of information form.

The researcher will then conduct the baseline assessment and the researcher will randomize the patient to condition while the participant is completing baseline measures. The researcher will inform the patient of the condition they have

been assigned after they have completed the baseline assessment.

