## **B. Informed Consent**

Patients and providers who are interested in participating will complete a screen for eligibility. As part of the screening process, the potential participants will also answer demographic questions to assess whether our recruitment efforts are reaching a diverse group and to assess the characteristics of participants in the research. Eligible participants will then proceed to the Informed Consent procedure with a researcher, though participants may choose to review the consent form on their own if they prefer. All participants will be provided with an overview of the study and disclosure regarding what will be asked of them using Informed Consent procedures. The Informed Consent form will describe the study procedures and clarify that the study is completely voluntary and that participants may decline to participate at any time. For the ED study, the information provided to patients about Jaspr will be limited until after randomization to guard against disappointment or other negative feeling if assigned to the CAU condition. Once randomized, patients assigned to the Jaspr condition will be provided with the supplemental consent form with complete disclosure of the study procedures and information about Jaspr. These patient participants will have the chance to ask questions about Jaspr and the Jaspr study condition and decide if they want to continue their participation in the study. Once initial eligibility is determined, potential participants will be given a brief description of the study and asked for their verbal consent to proceed with the Informed Consent discussion. The Informed Consent process will take place in person with a member of the research team. The Informed Consent process will take place remotely via telephone and/or internet with a member of the research team.

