All potential participants are informed during the Informed Consent procedure that participation is completely voluntary and that they may withdraw from the study at any time with no negative consequences. Eligible participants will receive a copy of the Informed Consent Form (via hard copy, or email). Participants will have the opportunity to read and review the consent form with the research staff, on their own, and/or review it with friends and family if desired. The researchers may use a high-level overview PowerPoint on their laptop computer to verbally and/or visually walk patients through the informed consent form and HIPAA Authorization (patients only). Study staff will be available to answer any questions or concerns the participants may have prior to signing and returning the consent form. For the ED study, patient participants assigned to the Jaspr condition will be walked through a supplement consent form with more information about the app, their signature will be collected for final consent, and they will receive an electronic or hard copy of the supplement consent form for their records.

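### For the ED repeated scales, the planned Time x Condition test is valid but leaves the baseline arm difference free, giving up precision that a common-baseline or baseline-adjusted model would recover at little cost

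*Combined protocol and SAP*

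**What the plan says.** Section 5.B (Analysis Strategy) enters condition and time as categorical dummy-coded predictors in a hierarchical linear model, and "the control conditions and baseline scores will serve as the reference category". The test is then defined: "The parameter of interest will be the Time X Condition interaction, and the Type III statistic will serve as an omnibus test". The visit-level reading follows: "Regression coefficients will indicate at which follow up time points the conditions showed differential change from baseline". The only other fixed effects named are site dummies; provider is a random effect. Neither a baseline covariate nor a common baseline mean is planned. The model can "include participants who are missing data at some time points", and the primary analyses are to be intent-to-treat.

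On timing, section 5.A (ED Study) says that "the researcher will randomize the patient to condition while the participant is completing baseline measures". Patients are told which condition they have "been assigned after they have completed the baseline assessment". Section 7.B adds a step for the Jaspr arm only: after randomisation these patients receive a supplemental consent, may "decide if they want to continue their participation in the study", and "their signature will be collected for final consent".

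Section 5.B (Statistical Power Considerations) powers the Time x Condition interaction: 24 patients for a medium effect (f read as .25), 72 with a design effect of 3.0, and at least 90 after 20% attrition, with a target of 120.

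**The concern.** With Condition in the model and baseline as the reference time, the Condition coefficient is the arm difference at baseline and is estimated from the data. Every interaction coefficient is then a difference in change from baseline, so it carries the sampling noise of both baseline means. In the ED study that noise need not be paid for. Patients complete baseline without knowing their arm, so any baseline gap is chance, and its expected value is known to be zero. A model that uses this estimates the same treatment effect with smaller variance. What is at stake is power, for the omnibus test and for each visit, on scales such as ideation, distress and self-efficacy. The outcomes recorded only once, such as restraint use and disposition, are outside this point.

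**Working it through.** **1. The plan's own figure.** G*Power's within-between interaction has noncentrality λ = N·m·f²/(1−ρ), with df m−1 and (N−2)(m−1). The documents give f, alpha .05, power .80 and equal groups. They give neither m (as used in the power calculation) nor ρ; m = 4 and ρ = .5 are assumed. At N = 24, λ = 24 × 4 × 0.0625 / 0.5 = 12, and power is 81.6%; N = 22 gives 77.5%. Then 24 × 3.0 = 72 and 72 / 0.8 = 90. The stated chain reproduces.

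**2. Variance under the two analyses.** Assume compound symmetry, unit SD, k follow-ups and n per arm. Apart from the factor 2/n, the covariance of the follow-up arm contrasts is:
- planned (free baseline): (1−ρ)(I + J)
- common or adjusted baseline: (1−ρ)(I + ρJ)

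The difference is (1−ρ)²J, which is never negative, so noncentrality cannot fall. For one visit the variance ratio is (1−ρ²)/[2(1−ρ)] = (1+ρ)/2, that is .65, .75 or .85 at ρ = .3, .5 or .7: a fall of 35%, 25% or 15%.

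**3. Power for an assumed effect.** Assumed, not in the documents: 0.5 SD, ρ = .3/.5/.7, three follow-ups, no design effect. Completers: 120 × 0.8 = 96, or 48 per arm. Worked at ρ = .5, omnibus:
- planned, sustained or one visit: λ = 24 × 0.25 × 0.75 / 0.5 = 9.0
- revised, sustained: λ = 24 × 0.25 × 1.2 / 0.5 = 14.4
- revised, one visit: λ = 24 × 0.25 × 0.8 / 0.5 = 9.6

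Power from noncentral F(3, 282), and from noncentral t(94) for a single visit (planned → revised, %):

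| | ρ = .3 | ρ = .5 | ρ = .7 |
|---|---|---|---|
| Single-visit contrast | 53.6 → 72.0 | 67.9 → 79.9 | 87.9 → 92.4 |
| Omnibus, sustained effect | 54.3 → 88.0 | 70.5 → 90.1 | 91.3 → 96.9 |
| Omnibus, fading (0.5, 0.25, 0) | 50.4 → 62.7 | 66.2 → 73.5 | 88.6 → 91.0 |
| Omnibus, one visit only | 54.3 → 59.8 | 70.5 → 73.5 | 91.3 → 92.2 |

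Section 5.B lists five ED occasions while counting four. With four follow-ups at ρ = .5 the omnibus figures are 69 → 91% (sustained) and 69 → 71% (one visit), so the picture is unchanged.

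**4. Validity.** A simulation of 6,000 trials at 72 evaluable patients (ρ = .5, no effect) gave omnibus false-positive rates of 5.2% planned and 5.1% adjusted.

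**5. Power at the plan's own effect size.** For a sustained or one-visit effect d, the planned λ at N = 24 (n = 12) is 6 × d² × 0.75 / 0.5 = 9d². Setting 9d² = 12 gives d ≈ 1.15 SD. At that size with 48 per arm and no design effect, planned power is already essentially 100%. With a design effect of 3.0 (n = 16 per arm, df from that n) and ρ = .5, omnibus power goes from 92% to 94% (one visit) or 99% (sustained), and single-visit power from about 88% to 95%.

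**The case against.** The best case for the plan is that nothing is wrong with it. Hypothesis 1 in section 3 is worded as a greater decrease from the initial session, and the planned test addresses exactly that with correct error rates. This stands, and it is why the point concerns efficiency only. It does not settle the choice, because when the arms have the same expected baseline, the difference in change and the baseline-adjusted difference estimate the same quantity.

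Second, the gains in the table rest on an effect size and correlations that the documents do not give. This also stands. At about 1.15 SD there is little to recover, and for an effect at a single visit the omnibus gain is small at any of the correlations used.

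Third, no model equation is given. If the team meant to omit Condition at baseline, the model would already be the common-baseline one. The text lists condition as a predictor and asks for a Type III interaction, so the free baseline is the natural reading, but it is an inference.

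Fourth, the researcher who conducts the baseline assessment also randomises during it, and so may know the arm before baseline ends. The baseline is mainly self-report, so the risk may be small, but it is an assumption of the revised model.

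Three stronger readings are tempting and are not supported:
- **That the sample size is wrong, or power is low.** The stated chain reproduces, and low power appears only under the smaller assumed effect.
- **That the loss matters more with design effects, which the plan expects.** Dividing n by design effects of 1, 1.5 and 3.0 (df kept at 94), the single-visit gain at 0.5 SD is 18, 16 and 9 points at ρ = .3, and 12, 12 and 8 at ρ = .5. Only at ρ = .7 does it rise (4.5, then 6.7 and 6.1).
- **That intent-to-treat covers only people who stop using the app, so Jaspr patients who leave at the supplemental consent would be dropped.** Section 5.B plans data from all participants at all time points and names app stoppers as one included group. An explicit sentence would help, but the plan does not exclude these patients.

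**Conclusion.** The point holds as an avoidable loss of efficiency for the ED repeated continuous scales. The planned test is not invalid and the sample size is not in error. Under compound symmetry the single-visit variance is 35%, 25% or 15% larger than necessary when expressed as a share of the planned variance, at correlations .3, .5 and .7. In power terms the gain runs from negligible (a large effect, or a high correlation with an effect at one visit) to 20 points or more (a sustained 0.5 SD effect at correlation .5 or below). The conclusion rests on four things: the reading of the dummy coding, baseline scores unaffected by assignment, the assumed correlations, and the assumed effect size. The direction does not depend on the last two; the size does. Because the baseline is already collected, the change is worth making before analysis.

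**What to change.** Choose one route for the ED repeated scales and name it in the SAP.

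- **Route 1, common baseline.** Keep baseline as a level of the outcome. Fit Time plus hand-coded Condition-by-follow-up dummies, with no Condition term at baseline. Test those dummies jointly and at each visit. Deleting Condition from a factor-coded model is not enough: with 2 arms and 4 times, that model still has rank 8 and the baseline stays free. The correct model has rank 7 before site terms, which serves as a check.
- **Route 2, baseline as covariate.** Model the follow-ups only. Test Condition and Time x Condition jointly, and report the arm difference at each visit. Do not keep Time x Condition alone as the test: among follow-ups only, it has 5% power against a sustained effect.

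Under either route, state that the baseline of every randomised ED patient is kept, with any follow-up they give. This includes Jaspr patients who stop at the supplemental consent, and is consistent with the intent-to-treat statement.

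Section 5.A places Telehealth randomisation in the enrolment call, before baseline. Apply the change there only if baseline is completed before the participant learns the assignment; otherwise leave that model as planned.

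The cost is a small change of model syntax, a sentence on the analysis set, and rewording of the named test in both Analysis Strategy and Statistical Power Considerations. No patients, visits or measures are added. The downsides are that the coding needs care and that the SAP must accept that the researcher's possible knowledge of arm during baseline does not affect the baseline scores.

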The ED study will also include provider participants who will be asked to complete a demographics survey and a brief interview about each of their index study patients after their intervention with the patient is complete. The brief interview will be administered in-person and assess the provider's feeling of preparedness for the assessment, the patient's degree of distress at the time of encounter, helpfulness of Jaspr's clinical support tool in discharge disposition determination, and risk assessment (if applicable).

ED study primary outcome variables include: suicidality (death by suicide, suicide attempts, suicidal ideation), ED/hospital admissions, discharge disposition, use of restraints while in ED (chemical, physical), intensity ratings of acute distress, self-efficacy in coping with distress, use of imminent distress intervention and coping skills, and helpfulness of their ED encounter. Jaspr condition-specific outcomes will be examined and reported descriptively. These include tools accessed during and after the ED visit, perceived usefulness and satisfaction of Jaspr brief intervention components, and usage of provider/patient apps and their features.

Telehealth study primary outcome variables include: suicidality (death by suicide, suicide attempts, suicidal ideation); Crisis-related healthcare utilization (ED visits, psychiatric hospitalization, calls to crisis line; crisis calls to therapist; Outpatient Satisfaction; Use of evidence-based interventions to reduce suicide risk (safety planning, lethal means management, behavioral skills). Secondary outcomes include: Reasons for living; Psychological distress (depression, anxiety, stress); Cognitions associated with suicide risk (hope, optimism, pessimism).

The primary hypotheses include:

1. Jaspr patients will report significantly greater decrease in suicidality and ED/hospital admissions than CAU patients from the initial session to follow-up assessments.
2. Jaspr patients will report significantly greater increases in self-efficacy in coping with acute distress, use of acute crisis tolerance skills, and perceived helpfulness of the care they receive compared to CAU patients.
3. Jaspr patients will report high levels of satisfaction with Jaspr.

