Follow up assessments will occur remotely via phone and internet 7-, 30-, and 90-days after baseline. At the pre-  
Evidence-Based Practice Institute | [name] | [contact] | [[contact]](mailto:[contact])

arranged time, the researcher will call the patient to conduct the study follow up assessment. The researcher will first send the patient a link to the online surveys via email and verbally remind the participant of their study ID. The researcher may also text the study ID to the patient if they prefer. The researcher will mute their phone and remain on the line as the patient completes the surveys. The researcher will unmute their phone and address any questions the patient may have as needed. Upon completion of the surveys, the researcher will then conduct the semi-structured interview.

The researcher will conclude the assessment by asking the patient to rate their level of stress, urge to self-harm, intent to kill self, intent to physically harm self using a 7-point Likert scale (based on [name] UWRAMP protocol). If the patient endorses a score of 5 or greater on urges to harm self or others or if a patient participant becomes distressed during or immediately after the follow up assessment, the researcher will do a warm hand off to Boys Town and inform the study PI immediately. Boys Town Hotline is staffed by a specialized team of crisis counselors trained in providing suicide risk assessments by telephone in accordance with the National Suicide Prevention Lifeline's Suicide Risk Assessment Standards. Boys Town Hotline will provide telephone crisis intervention services and will provide the research staff documentation, including information given during the call, the nature of the call, responses given, and other evaluative data elements, to the study PI within 24 hours. Boys Town will utilize their national internal database of service referrals to provide further action for the participant if deemed necessary. If the crisis counselor determines the participant's situation as life threatening, they will notify a senior counselor who will determine the level of assistance needed (i.e., if another party should be contacted, facilitation of contact with third party, and monitor the call while crisis counselor endeavors to remain actively engaged with the participant).

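### Suicide attempts, a primary component, are left to an omnibus Time X Condition test in which some arm-by-visit cells will probably be empty, with no rule for sparse events

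*Combined protocol and SAP*

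**What the plan says.** Section 3 (Introduction) sets the outcomes: "ED study primary outcome variables include: suicidality (death by suicide, suicide attempts, suicidal ideation), ED/hospital admissions", among others. The first primary hypothesis is that "Jaspr patients will report significantly greater decrease in suicidality and ED/hospital admissions than CAU patients from the initial session to follow-up assessments".

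The ED visits are set in section 5.A: "Follow up assessments will occur remotely via phone and internet 7-, 30-, and 90-days after baseline".

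Section 5.B (Analysis Strategy) fits hierarchical models with time and condition as categorical predictors. The control condition is the reference for condition, and for time "baseline scores will serve as the reference category". Then: "The parameter of interest will be the Time X Condition interaction, and the Type III statistic will serve as an omnibus test". Site dummies enter every analysis and provider is a random effect. On outcome type the plan says: "For each outcome, we will specify the correct distribution and compare fit indices to identify the covariance matrix best fitting the data".

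The power paragraph ties Hypotheses 1 and 2 to this rule. It considers "the ability to detect statistical significance on the key parameter of interest, the Time X Condition interaction", and says that 120 patients should give enough power for every outcome.

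The plan gives no attempt rate. It has no rule for empty cells, separation or non-convergence, and no single cumulative endpoint for attempts.

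**The concern.** An interaction between categorical time and condition suits suicidal ideation, which every patient scores at every visit. Attempts are few. Splitting them over three follow-up windows and two arms can leave a cell with no events. On a logit or log scale the coefficient for that cell then has no finite estimate and its standard error becomes very large. A Wald-type test gains almost nothing from that contrast, or the mixed model fails to converge.

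At stake is the answer to Hypothesis 1 for one of its most consequential components. A real difference could be reported as no differential change. If the model fails, the replacement would be chosen after the data are seen.

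**Working it through.** **Inputs from the documents.** 60 per arm (section 3); visits at 7, 30 and 90 days (section 5.A); two-sided 0.05, power 0.80, medium effect, design effect 3.0 and 20% attrition (section 5.B). Analysed per arm: 60 × 0.8 = 48.

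**Assumptions, because the documents are silent.** Attempt rates by day 90; non-overlapping windows between visits; events either front-loaded (25/35/40% over the windows) or proportional to days (7/23/60 of 90); baseline attempt prevalence 10% to 70%, equal in both arms. The post-treatment assessment, about two hours after baseline, is not counted as an attempt window. Clustering and within-patient correlation are ignored.

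**1. The plan's own figure.** For a within-between interaction, λ = f²·N·m/(1−ρ), with df m−1 and (N−2)(m−1). With f = 0.25, m = 4 and ρ = 0.5 (ρ is not stated), N = 24 gives λ = 0.0625 × 24 × 4 / 0.5 = 12 and power 0.816; N = 22 gives 0.775. Then 24 × 3 = 72 and 72/0.8 = 90. The figures reproduce. They are for a continuous outcome and use no event rate.

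**2. Empty cells, same rate in both arms.** P(at least one of six cells empty) = 1 − ∏ₜ[1 − (1 − r·wₜ)⁴⁸]², where r is the day-90 rate and wₜ the share of events in window t.

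| Rate by day 90 | Timing | P(cell empty), three windows | P(at least one empty) |
|---|---|---|---|
| 8% | front-loaded | 0.379, 0.256, 0.210 | 87% |
| 8% | by days | 0.741, 0.371, 0.072 | 98% |
| 15% | front-loaded | 0.160, 0.075, 0.051 | 46% |
| 15% | by days | 0.569, 0.153, 0.006 | 87% |

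The empty cells are mainly the early ones. With 20% versus 5% the lower-rate arm empties more often, and the probability is 86% (front-loaded) to 97% (by days).

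**3. What an empty cell does to a Wald contrast.** Take 3 of 48 in one arm and 0 of 48 in the other, with the zero set to 0.0001. The logits are −2.71 and −9.21, a difference of 6.50. The variance is 1/(48 × 0.0625 × 0.9375) + 1/(48 × 0.0001 × 0.9999) = 0.36 + 208.35 = 208.71. The contribution is 6.50²/208.71 = 0.20 before baseline variance is added. The 3-df critical value is 7.81.

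**4. Power for a four-fold difference, 48 per arm.** Wald and likelihood-ratio figures come from simulating the 3-df interaction in a saturated logit. For Fisher's exact test on any attempt by day 90, exact power is shown, with the range over simulated versions where one applies.

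| True rates | Wald | Likelihood ratio | Fisher |
|---|---|---|---|
| 20% v 5% | 0.3–1.9% | 19–39% | 48% (42–50%) |
| 10% v 2.5% | under 0.1% | 10–16% | 15% |
| 8% v 2% | under 0.1% | 7–10% | 8% (6% at lowest) |

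Most likelihood-ratio results at 20% versus 5% lie between 19% and 35%. The 39% arises with half the patients having a baseline attempt and front-loaded events. At 5% versus 1.25% Fisher has 2% and likelihood ratio about 3%.

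**5. Size needed for one cumulative comparison.** n per arm = [1.96·√(2p̄q̄) + 0.842·√(p₁q₁ + p₂q₂)]² / (p₁ − p₂)². For 20% versus 5%: (0.917 + 0.383)²/0.0225 = 75.1, so 76. For 10% versus 2.5%: (0.671 + 0.285)²/0.005625 = 162.3, so 163. Both are before design effect and dropout.

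**The case against.** Several points on the other side stand.

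- The plan says Type III, not Wald. The near-zero figures hold only for a Wald-type statistic. Mixed-model software commonly reports one, but the document does not commit to it. A reader might infer that the planned test has about 1% power; the text does not support that as a fact.
- One empty cell removes one contrast, not the whole omnibus test; the other contrasts still contribute. The simulation is also simpler than the planned model with site and provider terms.
- All attempt rates are assumed, and ED attempts may not be coded by window. Asking about events since the previous session is described only for the Telehealth study.
- Hypothesis 1 is worded for suicidality as a whole, ideation included. A reader might infer that it cannot be tested; for ideation it can.
- At control rates of 8% to 10% the proposed test is about as weak as the likelihood-ratio interaction. The shortfall there comes from rarity and sample size. A reader might infer that changing the test restores power; it does not.

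The plan's flexibility is a weaker defence. It allows for binary and count outcomes, promises a suitable distribution, and says only that many hypotheses concern change over time. A binomial or Poisson choice does not prevent an empty cell, and no fallback is named.

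**Conclusion.** The concern holds in a limited form. Under the only inferential rule given for change over time, attempts will probably meet at least one empty follow-up cell: 46% to 98% for day-90 rates of 8% to 15%, 48 per arm and non-overlapping windows.

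How badly the test then performs depends on the statistic. At 20% versus 5% a Wald-type test almost never rejects, a likelihood-ratio test has low power, and one cumulative comparison does better than either. At control rates of 10% or less no test has useful power. There the benefit is a risk difference with an interval, in place of a non-converged model or a misleading statement of no differential change.

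The arithmetic behind 24, 72 and 90 is sound on its own terms. It does not carry over to a rare binary outcome.

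**What to change.** In section 5.B (Analysis Strategy):

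- Exempt suicide attempts from the Time X Condition test and keep that model for suicidal ideation.
- Compare any attempt from randomisation to day 90 between arms once, by an exact or Firth-penalised method. Report the risk difference with a 95% confidence interval as the main result.
- List the 7-, 30- and 90-day counts by arm descriptively.
- State that site dummies and the provider random effect are dropped for this outcome when events are few. About 20 patients per site (section 4.F) means roughly 120/20 = 6 sites, too many terms for a handful of events.
- State how missed visits are handled: for example, an attempt reported at any completed visit counts, with a sensitivity analysis for incomplete follow-up.
- Use the same rule in the Telehealth study with its own visits (30 and 90 days). Expect little power: at 30 per arm, Fisher's test has 24% for 20% versus 5%.

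The cost is analysis wording only; visits, data collection and sample size do not change. The downsides are no formal test of when attempts differ, less adjustment for clustering, and the need for a missing-visit rule, since the planned model keeps patients with incomplete data. The text should also say plainly that the trial is not adequately powered for attempts.
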